Participants' social media data will be used to inform our collection and analysis of publicly available social media data (described elsewhere in the protocol), as well as additional analysis of participants' social media engagement and posted content. For our analysis of publicly available social media data, we will be able to better curate our data collection to include accounts followed and engaged with by our participants, as well as analyze what kinds of social media accounts and content different demographics of participants follow and engage with. For participant social media content (i.e., their own posts on social media), we will use state-of-the-art natural language processing techniques, such as sentiment analysis and word embeddings, and other metadata like post length to reduce such data to key pieces of metadata for analysis. This will inform us about how our participants post and share online about health-related topics, for example what kind of health-related topics they engage with the most and the language they use online when doing so, which can in turn inform how we choose to write nudge messages for the study.

There are no international sites.

19. Provisions to Monitor the Data to Ensure the Safety of Participants

This study poses minimal risk to participants.

20. Provisions to Protect the Privacy Interest of Participants

Participants will have the option to participate in the study or not as they choose. They will have the option of opting to be contacted to participate in other studies if they are interested. During the informed consent process, potential participants will be made aware of possible discomforts, who is able to access their information, and what kind of information they can access, how we plan to maintain their confidentiality, and the measures in place to protect their data. Potential study participants will have the opportunity to ask questions before they agree to participate in the study as well as other interactions (interviews, sharing social media data).

Personal identifiable data will be maintained on EU's REDCap account, in a dedicated, password protected OneDrive account, or as detailed above, limited personal identifiable information will be stored on the Georgia Tech server.

Social media data contribution

Those agreeing to contribute their social media data will be asked to provide their downloaded social media data to the study team as described above in Sections 14 and 18. For those that consent to participate provide their social media data, a unique identifier will be created when data is shared with the study team (See #19, Figure 2: Security and data design for technical applications supporting the project).

Data will be preserved through the end of the project, or until the period of time stipulated by the funding agency. No data will be maintained in medical records.

21. Economic Burden to Participants

There are not costs to participants related to their participation in the study.

22. Informed Consent

Individuals expressing interest in the study will be directed to the study site to complete an e-consent form. When conducting onsite recruitment, a study team member that is trained in conducting informed consent and is registered on the study IRB may be available to read through the informed consent form with the potential participant. In this case, the consent process will be performed in a private location, and any questions the participant has will be addressed.

Optional additional participation: Participants will be asked in the informed consent in-take questionnaire, if they would be willing to participate in an interview as a part of the study as well as to contribute their social media data. Participants are not required to be interviewed or contribute their social media data to participate in the study. During the informed consent, they will have the option to agree to be contacted about participating in an interview and/or to be contacted about contributing their social media data.

Before each interview, a trained interviewer will review the consent document with the participant and obtain verbal consent for both the interview and recording of the discussion.

Participant social media consent and contact

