Home-based testing may help people overcome barriers to testing (identifying where to get tested, scheduling and attending appointments, stigma).⁹ However, in order for it to be successful we need to understand the feasibility, acceptability, and sustainability of at-home testing as well as the perceived advantages and disadvantages of home-based testing compared to clinic-based testing among the high-risk population of individuals affected by or at risk for diabetes. This information can be used to create targeted behavioral “nudges”.¹⁰ Nudges are indirect suggestions and positive reinforcements designed to encourage certain choices. They may be a useful means of promoting acceptability and usage of home-based testing as well as increasing an understanding of and acceptability of other key preventive behaviors like COVID-19 vaccination. These targeted messages, sent via text messages, would be designed based on findings from PEACH 1 and the Georgia CEAL Study (1OT2HL156812-01/16-312-0217571-66105L). Behavioral nudges have been shown to have a noticeable effect on health behaviors and study recruitment,^{11,12} however, research testing the application of behavioral nudges relating to behavior change around disease prevention in a pandemic situation is needed.

4. Study Endpoints

Aim 1 Endpoint: Development of a suite of behavioral nudges text message designed to inform (Knowledge) and encourage (Persuade) study participants to perform COVID-19 testing at home or at other locations (primary behavior change focus) and other COVID-19 prevention activities (masking when needed, vaccination/boosters, etc.). Persuasive messaging will address perceived characteristics of COVID-19 testing and home-based testing (relative advantage, compatibility, complexity, trialability, observability) and be adapted to subgroups such as vaccination status and demographic data provided in the baseline survey.

Aim 2a Endpoint: Evaluation of uptake, usage, and perception of a community-based, adaptive intervention trial targeting individuals affected by diabetes through collaborations with community partner sites. The intervention entails reporting of COVID-19 testing via a text-based reporting system and targeted behavioral nudges delivered via text messages.

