Aim 2b: Evaluation of changes in vaccine uptake and hesitancy among study participants and family members post-implementation of the home-based testing platform as well as acceptability of nudges to affect behavior change.

5. Study Intervention/Design

PEACH² is a community-based, mixed methods, randomized, adaptive intervention trial, targeting individuals affected by diabetes. Study participants will be randomized into the PEACH² Intervention Arm or the Control Arm (*See Figure 1 below*). Participants may also opt to participate in an in-depth interview at the end of the intervention and/or to contribute social media data (see descriptions below).

All participants will be asked to complete surveys at baseline and again post intervention at Months 4 and end of follow-up at month 12. The intervention period will last 16 weeks. Baseline surveys will capture demographic data, history of COVID-19, diabetes and diabetes risk factors, views about COVID-19 risk factors and preventive behaviors, and experiences with COVID-19 testing; follow-up surveys at 4 and 12 months will collect information on intervention acceptability, COVID-19 testing, prevention, and vaccine behaviors and views from all participants.

[figure not shown]
PEACH² Intervention Participants: Intervention arm and control arm participants will be sent weekly text messages throughout the intervention period. Control arm participants will receive messages with general diabetes prevention/management information including messages on COVID-19 prevention, but these messages will not be tailored to the participant.

Intervention arm participants will receive weekly text messages with behavioral nudges targeted to their demographic and vaccination group targeting COVID-19 prevention behaviors. Results of qualitative interviews, social media reporting, and feedback from community partners from Project PEACH will be analyzed and used to draft group specific nudges for testing and other prevention behaviors. In weeks 4, 8, and 12, participants will be sent a series of text messages to determine if:

1. They had any COVID-19 symptoms in the past 4 weeks; and, if so:
2. They did a COVID test.

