Six hundred (n=600) participants will be recruited to participate in the study, and randomly assigned to participate in the intervention and control groups. Randomization will be done using a random allocation table created in SAS. Study participants that indicate they would be willing to participate in an interview will comprise the qualitative interview sampling frame. From total study sample, up to thirty in-depth interviews will be conducted with information rich individuals from the Control (N=10) and PEACH² Intervention (N=30) arms. Interview participants will be purposively selected based on data collected in the baseline survey. Demographics, vaccination status, prior experience with COVID-19 and testing, and testing reporting will be considered when compiling the contact list for interview.

The sample size of 600 was estimated using the following assumptions: (a) 80% power; (b) Alpha of 0.05; and (c) the percentage of participants receiving a COVID-19 test in the past month in the control arm would be equal to the percentage of the Georgia population getting a PCR test for COVID-19 in the month of June: 3.44 (standard deviation [SD] 0.49). Using these assumptions, a sample size of 520 (260 per study arm) will be powered to see a 4.5% increase in the percentage of individuals receiving COVID-19 test in the intervention arm compared to controls. We plan to randomize 600 individuals to allow for attrition.

Social media analysis enrollment

Given the complexity of the data download and upload process for participants to complete, we anticipate a significant amount of attrition. Thus, we will conduct individual phone call follow-ups with a selected subset of participants who had consented to being contacted about sharing their social media data for the study, but have not at that time completed the social media data contribution process. As we are conducting this data collection as a proof-of-concept, participants chosen for individual follow-up would be sampled (out of those who indicated use of a social media platform of interest) to cover different demographic groups and other characteristics that are represented by the broader participant pool, and from both the control and intervention arms. We aim to conduct individual follow-up with up to 50 participants.

14. Recruitment Methods

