Participant survey data will be exported by a member of the study team with access to REDCap and uploaded via HTTPS via 2-Factor VPN to one of two databases which support the Dashboard and the Nudge Platform. This export will include a “participantId”, which is a pseudo ID unique to this study and has no relationship to other participant identifiers.

The Limited Study Database (DB) will be maintained separately from both the social media data collection and analytics platform, and from the Nudge Database (DB) to minimize risks and control access. The Limited Study DB used by the Dashboard will contain the participantId, age in years, race, ethnicity, gender, testing history, vaccine status, diabetes status, study enrollment status and history; if provided, participant social media account and activity data will be maintained in the Limited Study Database following collection and anonymization. The Nudge DB will contain the participantId, cell phone number, first name, nudge response, nudge status, and an optional REDCap survey link.

The Nudge Platform will only be accessible via the Dashboard. The Dashboard will implement role-based access controls to limit who is able to send nudge messages to approved study staff. Operators of the Dashboard will have access to nudge responses and the status of a nudge message, but no operator will have direct access to the participant phone numbers, first name, or personalized survey link (if used). Nudges will be delivered to users via the Twilio SMS text messaging platform using secure communications. Nudge responses will be delivered via secure callbacks to the Nudge Platform via Twilio.

Should the study include social media data collection from participants, this will be collected via a secure website using a non-reversible encrypted user key which can only be mapped to the participantId (or other information) in the Limited Study DB. Both the Nudge Dashboard and Platform will be developed and maintained by the Georgia Tech study team. Access will be restricted to select members of the study team. All access to the Dashboard by EU, MSM or GT will require a Georgia Tech account or guest account, sponsored by the GT sub-award Co-PI. Access will require the use of 2-Factor authentication to a VPN and 2-Factor authentication to the web Dashboard. No public access will be possible. The Nudge Platform will only support access via the Dashboard. Certificate-based authentication for all transactions with the Nudge

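### No analysis model is named for the randomised testing comparison; pre-specify a risk difference adjusted for baseline testing history and vaccination status, a small gain that does not repair the power

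*Combined protocol and SAP*

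**What the plan says.** Sections 13 and 25 of the combined protocol and SAP give the only description of the randomised comparison. They assume 80% power, an alpha of 0.05 and a control-arm past-month testing percentage of "3.44 (standard deviation [SD] 0.49"). They conclude that 520 participants (260 per arm) suffice for a 4.5% "increase in the percentage of individuals receiving COVID-19 test in the intervention arm compared to controls". Six hundred are to be randomised to allow for attrition. Section 25 adds a two-stage recalculation of sample size, without a rule.

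The baseline data include two natural covariates:

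- Section 5: the baseline survey covers "views about COVID-19 risk factors and preventive behaviors, and experiences with COVID-19 testing".
- Section 4 (Aim 1 endpoint): messages are adapted to subgroups such as "vaccination status and demographic data provided in the baseline survey".
- Section 18: the study database behind the dashboard holds, among other items, "testing history, vaccine status, diabetes status".

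The uses stated for these variables are tailoring messages, supporting the dashboard and choosing interviewees. Section 18 has data analysis in its title, but covers data handling, security and social media text analysis. The checklist in Section 28 asks that section for statistical procedures and is ticked as done. Randomisation is by an allocation table produced in SAS (Section 13); stratification is not mentioned.

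**The concern.** Testing before randomisation plausibly predicts testing afterwards, and vaccination status helps decide which messages the intervention arm receives. Adjusting a randomised comparison for such variables generally improves precision and removes the effect of chance imbalance in them, without introducing meaningful bias. Here both variables are on file and neither is assigned to the analysis. Two things are at stake: some precision, in a trial whose power is below what it states, and protection against choosing covariates and effect measure after the results are seen.

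**Working it through.** **1. The plan's own figure.** Inputs from Section 13: control rate p1 = 0.0344, 260 per arm, alpha 0.05, power 80%. Sidedness is not stated, so two-sided is assumed. The 4.5% is read as absolute, so p2 = 0.0794 and the mean rate is p̄ = 0.0569.

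Power = Φ{[(p2 − p1)√n − 1.96√(2p̄(1 − p̄))] / √(p1(1 − p1) + p2(1 − p2))}

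= Φ{[0.045 × 16.125 − 1.96 × 0.3276] / 0.3261} = Φ(0.256) = **60.1%**.

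Required n per arm = [(1.96 × 0.3276 + 0.8416 × 0.3261) / 0.045]² ≈ **415**.

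The stated 260 is not reproduced. One-sided, power is 71.7%. If all 300 per arm are retained, two-sided power is 66.3%.

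**2. What adjustment can add.** For one binary baseline covariate with prevalence q, and later testing RR times as likely in those who have it, the share of variance explained is approximately

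R² = [p̄/(1 − p̄)] × (RR − 1)² q(1 − q) / [1 + (RR − 1)q]².

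The adjusted analysis then behaves like an unadjusted one with n/(1 − R²) per arm. The documents give neither q nor RR, so both are assumptions.

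| Control vs intervention | q | RR | R² | Power at 260 per arm, crude → adjusted |
|---|---|---|---|---|
| 3.44% vs 7.94% | 3.44% | 1.5 | 0.0005 | 60.1% → 60.1% |
| 3.44% vs 7.94% | 3.44% | 4 | 0.015 | 60.1% → 60.8% |
| 3.44% vs 7.94% | 20% | 4 | 0.034 | 60.1% → 61.6% |
| 10% vs 14.5% | 10% | 4 | 0.067 | 34.6% → 36.7% |
| 10% vs 17.5% | 10% | 4 | 0.076 | 70.1% → 73.5% |
| 20% vs 30% | 20% | 3 | 0.109 | 75.1% → 79.8% |

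At RR = 4, R² is largest at q = 0.2, so 0.034 is the ceiling for one such covariate at the planned rates. The last three rows use rates that are not in the documents. They are shown because 3.44% is a statewide PCR figure for one month, while the Aim 1 endpoint also covers testing at home.

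**3. Simulation check.** With 20,000 trials per scenario at 260 per arm and standardisation over baseline-testing strata, crude and adjusted power were 61.1% and 62.1% (second row), 34.9% and 37.3% (fourth), 70.9% and 74.2% (fifth), and 75.7% and 80.6% (sixth). Type I error in three null scenarios was 4.8–5.2%. In a separate run, with a linear model at the planned rates and RR = 1.5, there was no gain: the variance ratio was 1.003 and power went from 61.1% to 61.2%.

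**4. Can adjustment close the power gap?** Reaching 80% would need R² = 1 − 260/415 = 0.37, or 1 − 300/415 = 0.28 with no attrition. At R² = 0.034 the requirement is still 415 × 0.966 ≈ 401 per arm.

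**5. Sparse data.** If 3.44% tested in the month before baseline, that is 0.0344 × 260 ≈ 9 people per arm. With RR = 4, their later risk is 4 × 0.0344/1.1032 = 0.125 in the control arm and 4 × 0.0794/1.1032 = 0.288 in the intervention arm. The chance that no baseline tester in either arm has the outcome is (1 − 0.0344 × 0.125)^260 × (1 − 0.0344 × 0.288)^260 ≈ 0.33 × 0.075 ≈ 2.5%. With no treatment effect it is 0.33² ≈ 11%. In those datasets an ordinary logistic model has no finite coefficient for that covariate.

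**The case against.** The strongest reply is that sample-size text does not fix the analysis. Sizing a trial on two proportions is common and compatible with an adjusted analysis later. That stands. A reader might infer that the plan has chosen a crude test and so discards precision; the documents do not support this, because they choose no analysis at all. Nor do they show that randomisation is simple: they are silent on blocking and stratification.

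The second reply is that the gain is close to nil at the only control rate the protocol gives. This largely stands. The more attractive example, 20% versus 30%, rests on a control rate and an effect that the documents do not contain, and every figure depends on an assumed RR.

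The third reply is that the covariate may not exist in the form one would want. Sections 5 and 18 refer to testing experiences and testing history; neither confirms a past-month item at baseline. This limits which variable can be named, but not the recommendation to adjust for what is recorded.

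None of these replies removes the point. No adjusted analysis is specified, suitable variables are already collected, and naming them in advance costs almost nothing.

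**Conclusion.** The point holds as a modest improvement in method. The plan names no model for its only powered comparison and plans no adjustment, although baseline testing history or experience and vaccination status are on file. At 3.44% versus 7.94%, adjustment reduces variance by about 0–4% for RR up to 4. Power rises by about 0.5–2 points when RR is near 4, and hardly at all at 1.5. At control rates of 10–20% the reduction is about 6–10% (10.9% by formula in the most favourable row) and the gain 2–5 points. These sizes assume one binary covariate of unknown strength; the documents give no basis for adding a figure for vaccination status.

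A reader might also infer that adjustment would restore the stated 80% power. It would not: the R² required is roughly ten times the 0.034 ceiling found above. Power of about 60% at 260 per arm is a separate defect.

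**What to change.** Add a short primary-analysis statement:

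- Compare arms as randomised on the marginal (standardised) risk difference in COVID-19 testing, with a robust confidence interval.
- Adjust for baseline testing history as actually recorded, and for baseline vaccination status. Use past-month testing only if the survey asks about it.
- Name a method that is stable with few events: for example, linear risk-difference regression with robust standard errors, or penalised logistic regression followed by standardisation.
- Fix the covariate categories before outcome data are examined by arm.
- Report the crude difference in percentages alongside.

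The cost is a paragraph and slightly more analysis work. No new data are needed if the recorded testing history is used; a past-month item, if absent, would mean a survey change. Separately, restate the power and sample size in Sections 13 and 25, and give the two-stage recalculation a rule. Adjustment should not be offered as a substitute for either.

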Participants will have the option to contribute additionally to the study by sharing their own social media data with the study. We will focus on the following data from participants' Facebook, Instagram, and X (Twitter) accounts: the accounts, pages, and groups they follow; other accounts' content that they have engaged with; and their own posted content related to COVID-19 and health. Social media data collected from participants will be used to inform our collection and analysis of publicly available social media data (described above) as well as additional analysis of participants' social media engagement and posted content. This will allow us to better curate our data collection to include accounts followed and engaged with by our participants as well as analyze what kinds of social media accounts and content different demographics of participants follow and engage with. For participant social media content (i.e., their own posts on social media), we will use state-of-the-art natural language processing techniques, such as sentiment analysis and word embeddings, and other metadata like post length to reduce such data to key pieces of metadata for analysis.

6. Procedures Involved

Study participants in PEACH² will be asked to complete baseline surveys as well as follow-up surveys at completion of the intervention period (Month 4) and again at Month 12, about their experiences and perceptions of COVID-19 testing and vaccination. Survey data will be captured using REDCap. Selected participants that agree to be contacted on their informed consent form may also be invited to participate in semi-structured interviews. These will be conducted over a secure Zoom account. Semi-structured in-depth interviews will explore acceptability and experiences with the text messaging program.

Participants will also be asked if they are willing to contribute data from their social media posts (detailed methods below). Those that are willing will receive an automated link from REDCap with additional information about participation in the social media part of the study as well as an informed consent form specific to that part of the study. Participants will be given the option to share or not share data from the different platforms they use; their consent for this social media data collection will have no implications for their participation in the rest of the study.

Participant social media data contribution

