23. HIPAA

This study will not record identifiers from medical records of living or non-living subjects. A unique study identifier will be created when the participant completes the informed consent and enrolls in the study. PHI collected is self-reported data and will be used to assign the participant to a nudge group based on how they are affected by or at risk for diabetes. Identifiable study data will be maintained in the study's secure REDCap project database, which is password protected and HIPAA compliant and in Georgia Tech's Nudge Platform. Only authenticated study team members that have assigned user privileges will have access to PHI.

24. Setting

Potential participants will be recruited through existing EU, MSM and GT partnerships with community based (RX MTM) and faith-based organizations (Big Miller Grove Baptist Church, Elizabeth Baptist Church), Diabetes clinics (Grady Diabetes Center) and FQHCs that serve communities at risk across Georgia. Partners will promote the study at their sites via in-person presentations, flyers and distribution of palm cards, or to their patients (clients), and direct them to the study website to complete the e-informed consent and online eligibility and study enrollment forms. Those that enroll will agree and consent to utilize their own cellular devices

to receive behavioral nudge text messages and submit responses about whether they had COVID symptoms in the past 30 days (Y/N) and if they took a COVID-19 test (Y/N).

The study will continue the community advisory board (CAB) started during Project PEACH, which is comprised of members of the partner organizations, community investigators, and local stakeholders. Partner organizations involved in Project PEACH, but not PEACH2, will be informed that they can choose to continue in an advisory role or leave the group as they wish. Any new community organizations that join the study team will have a member seated on the CAB. Members of partner organizations will not be involved in recruitment beyond the distribution of promotional information. Their participant-related contact will be limited to assisting participants to access the e-informed consent form.

25. Resources Available

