Facilities: Emory University (EU), Georgia Institute of Technology (GT) and Morehouse School of Medicine (MSM) all house institutes and centers that engage with or include the other partner institutions. The PEACH² study PIs and team members are members of the **Georgia Center for Diabetes Translation Research (GCDTR)** with PIs (EU: [name], [name] MSM: [name]; GT: [name]) also serving on or leading the GCDTR Cores (Design and Evaluation; Engagement and Behavior Change; Disparities; Enrichment Program). GCDTR Cores afford access to subject area expertise relevant to the study, including diabetes and related risk factor epidemiology, biostatistics, engineering, and demography. Other EU, GT, MSM collaborations and centers provide a rich pool of subject matter expertise and community partners that can be leveraged for this project. The Georgia Institute of Technology team members are also members of the **GT Institute for People and Technology** and **GT Center for Health and Humanitarian Systems**. The MSM team members are PIs and key investigators of the **Georgia CEAL**, the **GCTSA Community Engagement (CE) Program** and the **MSM Prevention Research Center (PRC)**. Further, each institution is involved in other RADx projects, such as The Atlanta Center for Microsystems Engineered Point-of-Care Technologies (ACME POCT)'s Rapid Acceleration of Diagnostics (RADx) Validation Core (U54 EB027690-02S1) at EU, Children's Healthcare of Atlanta. GT assesses user needs for novel COVID-19 devices and evaluates point of care devices for performance (EU/GT).

Study Team: PEACH2 PIs and study team members began collaborating during Project PEACH and will utilize lessons learned and gaps identified through Project PEACH as well as leverage community partnerships and infrastructure for this study.

Sample Size: The sample size of 600 was estimated using the following assumptions: (a) 80% power; (b) Alpha of 0.05; and (c) the percentage of participants receiving a COVID-19 test in the past month in the control arm would be equal to the percentage of the Georgia population getting a PCR test for COVID-19 in the month of June: 3.44 (standard deviation [SD] 0.49). Using these assumptions, a sample size of 520 (260 per study arm) will be powered to see an 4.5%

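### Must the plan change because the past-month testing outcome is tied to no survey wave, and Sections 5 and 24 describe the text question differently?

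*Combined protocol and SAP*

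**What the plan says.** **The sizing outcome.** Section 13 assumes a control value for "the percentage of participants receiving a COVID-19 test in the past month", set at 3.44. It plans 260 per arm to detect a 4.5% increase and randomises 600 to allow for attrition. Section 25 repeats this: "the percentage of participants receiving a COVID-19 test in the past month in the control arm". Neither section names a survey wave. In Section 4, the Aim 1 endpoint speaks of messages encouraging participants "to perform COVID-19 testing at home or at other locations (primary behavior change focus". The Aim 2a endpoint covers uptake, usage and perception, without a proportion or time point.

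**The surveys.** Section 5: "follow-up surveys at 4 and 12 months will collect information on intervention acceptability, COVID-19 testing, prevention, and vaccine behaviors and views from all participants". Section 6 times them as "follow-up surveys at completion of the intervention period (Month 4) and again at Month 12". The protocol text gives no recall window for the testing item.

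**The texts.** Section 5 says that both arms "will be sent weekly text messages throughout the intervention period". Within the description of the intervention-arm messages, it adds a series at weeks 4, 8 and 12 to find out whether "They had any COVID-19 symptoms in the past 4 weeks; and, if so" they did a test. Those reporting symptoms but no test then receive further testing nudges. Section 24, in a summary of the setting, says that those who enroll will "submit responses about whether they had COVID symptoms in the past 30 days (Y/N) and if they took a COVID-19 test (Y/N".

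**The concern.** The past-month percentage is the only quantified between-arm comparison in the document, so a reader expects it to have a source, a time point and a denominator. Two survey waves could supply it, and they answer different questions: one is about behaviour while messages are arriving, the other about persistence months later. If either could be reported after the results are seen, the false-positive risk rises above 5%.

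The texts add a second worry. If the test question is asked only after reported symptoms, the replies cannot give a percentage of all participants. A comparison of arms among the symptomatic would condition on something reported after randomisation, which COVID-focused messages might themselves alter. Section 24 reads as though the question is asked without that condition, and of everyone. A reader could then wonder whether the texts are meant to be the outcome source after all.

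**Working it through.** **1. The plan's own figure.** Reading 4.5% as percentage points gives 3.44% versus 7.94%. With two-sided 5%, 80% power and pooled null variance,

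n per arm = [1.960·√(2·p̄·(1−p̄)) + 0.842·√(p₁(1−p₁) + p₂(1−p₂))]² / (p₂−p₁)², with p̄ = 0.0569.

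This gives 415 per arm, not 260. Power at 260 per arm is 60.1%. That shortfall is a separate matter and does not depend on which survey supplies the outcome. The 60.1% is used below only as a yardstick.

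**2. Which source can supply the sizing outcome?** It needs a testing answer from all participants in both arms.

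| Source | Who is asked | Test question conditional on symptoms? | Stated use |
|---|---|---|---|
| Month-4 survey (Sections 5, 6) | all participants | no condition stated | follow-up data |
| Month-12 survey (Sections 5, 6) | all participants | no condition stated | follow-up data |
| Texts, weeks 4, 8, 12 (Section 5) | in the intervention-arm description | yes | choosing the next message |

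Only the surveys meet the requirement.

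**3. Which survey fits an effect of the messages?** The intervention lasts 16 weeks = 112 days. Take a 28-day look-back.
- Month 4 at completion of the intervention (day 112): the window is days 84 to 112, so 28/28 = 100% lies inside the intervention.
- Month 4 taken instead as a calendar date (365.25/3 = day 121.75): the window opens on day 93.75, so (112 − 93.75)/28 = 65% lies inside.
- Month 12 (day 365.25): the window opens on day 337.25, which is (337.25 − 112)/7 = 32.2 weeks after the intervention ends, so 0% lies inside.

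Section 6 describes the first case. On the protocol's own wording, Month 4 measures the intervention and Month 12 measures what remains of it.

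**4. How large is the 4-week versus 30-day difference?** Both look-backs belong to the symptom item; neither section gives the test item one. Suppose nevertheless that the difference applied to the sizing outcome, with 3.44% and 7.94% as 30-day rates under a constant hazard. Over 28 days:
- control: 1 − (1 − 0.0344)^(28/30) = 3.21%;
- intervention: 1 − (1 − 0.0794)^(28/30) = 7.43%.

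Power at 260 per arm is 57% instead of 60%.

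**5. The feared harms, with their assumptions.**
- Testing both waves at 5% and reporting either: 1 − 0.95² = 9.75% if independent, about 9.1% at an assumed correlation of 0.5. No section proposes this.
- Comparing arms among the symptomatic, with 3.44% tested in each arm, all tests by symptomatic people, and assumed symptom reporting of 10% versus 12%: 3.44/10 = 34.4% against 3.44/12 = 28.7%, a spurious fall of 5.7 points. This also needs controls to be asked, and no section proposes the comparison.

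**The case for a change.** The best case for a change is that pre-specification exists to remove choices, and here one choice is open. Two surveys qualify and the text picks neither. Section 18 carries data analysis in its title but describes no between-arm testing analysis. The two-stage sample-size recalculation in Section 25 also needs an outcome and a time point, and names neither. A questionnaire might give the recall window but would not normally say which wave is the outcome. One sentence would close the gap at almost no cost.

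The facts in that case stand: the link between the sizing outcome and a wave is not written down, and Sections 5 and 24 do not match on the symptom condition or on who is asked. What does not follow is that the trial would go wrong without the sentence. The sizing text already gives a past-month window, and the surveys already reach all participants. Section 6 already places one of them at the end of the intervention. The stated primary objective is feasibility, acceptability and sustainability, which weakens an argument built on confirmatory error. Section 24 is a short summary that leaves out the symptom condition without denying it. Figure 1 and the survey instruments are not available here and may hold the detail.

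**Conclusion.** No change to the plan is called for. The omission is real, but it is missing detail with an evident reading: testing in the past month, from the Month-4 survey, among all randomised participants, with Month 12 showing persistence. An analyst following the protocol would reach that comparison, and it would be sound. The differences between Sections 5 and 24 are a drafting mismatch in a process question. Reconciling them alters no stated result, and even if the look-back difference carried over to the outcome it would be worth about 3 points of power (60% to 57%).

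The larger figures, a 9.75% false-positive chance and a spurious 5.7-point gap, each need an analysis that the plan does not contain. The conclusion rests on two assumptions: that the Month-4 survey is fielded at completion of the intervention, as Section 6 says, and that the text replies keep their one stated use. If symptom-conditioned replies were later used to compare arms, the concern would become a real one.
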